### **8.2.3 Supportive and sensitivity analyses of the secondary efficacy variables**

Descriptive statistics (number of available observations [n], mean, median, standard deviation, minimum and maximum) will be provided for all secondary efficacy variables. The descriptive analyses will be covered in the tables summarizing the variables over time.

Sensitivity analyses of the secondary binary efficacy variables (ASAS40 at Weeks 12 and 52) as described in [Section 8.2](#) will be as follows:

- Including observed data at Week 52 (or Week 12 as applicable): As described for the primary efficacy variable in [Section 8.1.3.1](#).
- Multiple imputation: As described for the primary efficacy variable in [Section 8.1.3.2](#). Note that as ASAS40 is a composite of 4 different variables, the multiple imputation procedure will be performed on each of these components, and the ASAS40 response will be derived prior to Step 5 based on the multiply imputed datasets.
- Reference-based multiple imputation: As described in [Section 8.2.2.2](#).
- Observed case analysis: As described for the primary efficacy variable in [Section 8.1.3.4](#).

The sensitivity analyses of secondary continuous efficacy variables (the change from Baseline in BASDAI and BASFI at Weeks 12 and 52, the change from Baseline in the SI joint SPARCC

score at Week 12, the change from baseline for ASQoL at Week 52 and the change from baseline for Nocturnal Spinal Pain at Week 52) will be as follows:

- Including observed data at Week 52 (or Week 12 as applicable): As described for the primary efficacy variable in [Section 8.1.3.1](#)
- Multiple imputation: As described in [Section 8.2.3.1](#)
- Observed case analysis: As described for the primary efficacy variable in [Section 8.1.3.4](#).
- Last Observation Carried Forward (LOCF): If there is missing data at the time point of interest, the last available post-Baseline measurement will be carried forward to that time point (including scheduled or unscheduled visits). This will not apply for the analysis of SI joint SPARCC score at Week 12 since there are no measurements collected between Baseline and Week 12.

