## **2.4 Determination of sample size**

Subjects will be randomized in a 1:1 ratio to the CZP 200mg Q2W and placebo treatment groups. The expected response rates for ASDAS-MI at Week 52 are 40% and 20% for CZP and placebo, respectively. A total sample size of 300 (150 subjects per treatment group) provides 95% power to detect a statistically significant difference in the ASDAS-MI response rate at Week 52 between CZP and placebo based on a 2-sided significance level of 0.05.

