As it is the raw ASDAS scores being imputed, the shift size (delta) will start with 0, 0.1, 0.2, 0.3, 0.4, 0.6, 0.8, 1.0, 1.2, 1.4, 1.6 and 1.8. Further values for delta may be investigated depending on the results obtained in order to determine the point at which the results are no longer significant.

When tipping point analyses is applied to ASAS40 response, the imputation will be done on the raw components before assessing the imputed results for ASAS40 response. The same delta shifts (0, 0.1, 0.2, 0.3, 0.4, 0.6, 0.8, 1.0, 1.2, 1.4, 1.6 and 1.8) will be investigated applied to the raw components (each of which are on a scale from 0 to 10) prior to calculating ASAS40 response. Further values for delta may be investigated depending on the results obtained.

This will be done once for each of the 100 datasets. The same delta value will be assumed for all visits.

3. The ASDAS change from Baseline to Week 52 will be calculated using the complete datasets (with no missing data) and categorized as: ASDAS- MI or not ASDAS-MI.
4. For each of the 100 imputed datasets (identified by `_imputation_` variable), the odds ratio of the treatment comparison and corresponding 95% CI for ASDAS-MI responder rates at Week 52 based on the observed data will be estimated using a logistic regression model with factors of treatment group, region, and MRI/CRP classification (MRI+/CRP+; MRI+/CRP-; MRI-/CRP+) and Baseline as a covariate in the same manner as the primary endpoint analysis.
5. The results from these analyses will be combined into a single inference using SAS PROC MIANALYZE. The parameter estimate and 95% CIs will be back transformed (using the exponential function) to give the odds ratio and CI for the CZP vs PBO comparison. This will be presented alongside the p-value from the proc mianalyze.
6. Steps 2 through 5 will be repeated using different values for the shift parameter as specified in step 2. Following the final Step 5, for each value of delta, the odds ratios, CIs and p-values will be presented in a single table with the associated delta value which was applied in the analysis.

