### 8.2.1 Derivation of secondary efficacy variables

#### 8.2.1.1 Assessment in Axial SpondyloArthritis international Society response criteria (ASAS20/40, ASAS5/6, and ASAS partial remission)

The ASAS20 response is defined as an improvement of at least 20% and absolute improvement of at least 1 unit on a 0 to 10 NRS in at least 3 of the 4 following domains (Anderson, 2001):

- Patient's Global Assessment of Disease Activity;
- Pain assessment (the total spinal pain NRS score);
- Function (represented by the BASFI);
- Inflammation (the mean of the BASDAI questions [Q] 5 and 6) concerning morning stiffness intensity and duration)

and absence of deterioration in the potential remaining domain [deterioration is defined as a relative worsening of at least 20% and an absolute worsening of at least 1 unit].

ASAS data collected after the discontinuation of double-blind study treatment will be treated as missing in the original data set.

The ASAS criteria for 40% improvement (ie, ASAS40) are defined as relative improvements of at least 40% and absolute improvement of at least 2 units on a 0 to 10 NRS in at least 3 of the 4 domains and no worsening at all in the remaining domain.

The ASAS 5/6 response is defined as at least 20% improvement in 5 of 6 domains, which includes spinal mobility (i.e., lateral spinal flexion of the BASMI) and CRP as more objective measures (Brandt et al, 2004). For CRP values below the lower limit of quantification (<4mg/L), half the lower limit (2 mg/L) will be used as the imputed value.

The ASAS partial remission response is defined as a score of  $\leq 2$  units on a 0 to 10 unit scale in all 4 domains.

ASAS40 response at Week 12 and Week 52 are secondary efficacy endpoints.

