### **8.2.2.2 Primary analysis of continuous secondary efficacy variables**

The continuous BASDAI, BASFI, ASQoL and Nocturnal Spinal Pain score at each visit will be calculated using the methods described in [Sections 8.2.1.2, 8.2.1.3, 8.2.1.6 and 8.2.1.7](#). Missing data (including data excluded due to subjects discontinuing double-blind study treatment) at each visit will be handled via reference based multiple imputation as described below:

The reference-based multiple imputation assumes that the statistical behavior of the CZP and placebo-treated subjects after discontinuing study medication becomes that of the placebo-treated subjects. Data collected after discontinuation of the double-blind study treatment for both the CZP and placebo groups will be considered missing. Multiple imputations are used to replace missing outcomes for drug- and placebo-treated subjects who discontinued using multiple draws from the posterior predictive distribution estimated from the placebo arm. For binary efficacy variables (ASAS40 at Weeks 12 and 52), imputation will be done on the raw components before assessing the imputed results for ASAS response. For continuous efficacy variables (change from Baseline in BASDAI and BASFI at Weeks 12 and 52, change from Baseline in the SI joint SPARCC score at Week 12, change from baseline in ASQoL and Nocturnal Spinal Pain at Week 52), imputation will be done on the raw scores prior to calculating the change from Baseline.

1. For subjects with a non-monotone (intermittent) missing pattern, MCMC will be used to impute their missing intermittent scores including treatment, region and MRI/CRP

classification as explanatory variables. This will be done 100 times in order to provide a dataset with monotone missing limiting imputation to in range results.

After this step there will be 100 datasets containing all subjects however the only missing data will be a monotone missing data pattern. A variable called “\_imputation\_” will identify each of the 100 imputed datasets output.

2. The remaining missing data for all subjects with a monotone missing data pattern will be imputed using regression using the placebo-treated subjects arm only to impute missing data for both placebo and CZP treatments. The model will contain region, MRI/CRP classification and measurement from previous visit(s) as explanatory variables. This model will be run once for each of the imputed datasets limiting imputation to in range results.

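### The ASAS40 sensitivity analyses impute the four components by models that name no other component, which weakens their correlation and makes the derived response too rare at low-to-moderate component success

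*SAP*

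**What the plan says.** **Multiple imputation under MAR.** For ASAS40 at Weeks 12 and 52, SAP Section 8.2.3 (and Section 4.2.2) refers back to the ASDAS procedure and adds: "Note that as ASAS40 is a composite of 4 different variables, the multiple imputation procedure will be performed on each of these components". The response is derived from the completed data sets. The procedure referred to, Section 8.1.3.2, handles one variable. Both its MCMC step and its monotone regression list treatment arm, region, MRI/CRP classification and that variable's earlier values.

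**Reference-based imputation.** Section 8.2.2.2 also works on raw components for ASAS40, with the regression fitted on placebo subjects only: "The model will contain region, MRI/CRP classification and measurement from previous visit(s) as explanatory variables".

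**Tipping point.** Section 8.1.3.3 imputes by treatment group from earlier values, MRI/CRP class and region. For ASAS40, "the imputation will be done on the raw components before assessing the imputed results for ASAS40 response".

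**The endpoint.** Section 8.2.1.1 asks for a gain of 40% and of 2 units in three or more of the four domains, with the fourth not worse than before.

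**Where these analyses sit.** In both testing hierarchies of Section 8, ASAS40 is tested by the composite (non-responder) analysis. Sections 4.2.1, 8.1.3 and 8.2.2.1 repeat the full set of sensitivity analyses for ASAS40 at Week 12, which is the primary variable for Canada and other requesting authorities.

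**The concern.** ASAS40 is a joint event across patient global, spinal pain, BASFI and morning stiffness. Four models can each reproduce the distribution of their own component and still give the wrong response rate, because the rate also depends on how the components move together at the imputed visit. If each component is drawn with its own independent residual, the only shared signal left is what the separate histories carry.

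At stake is the credibility of three analyses meant to test whether the ASAS40 result survives different missing-data assumptions. All three inherit the same feature, so none of them can reveal it in another.

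**Working it through.** **1. The plan's own figure.** Section 2.4 is the only place with a calculable figure: "A total sample size of 300 (150 subjects per treatment group) provides 95% power" for assumed ASDAS-MI rates of 40% on CZP and 20% on placebo, with equal allocation and a two-sided 5% level. The pooled normal approximation gives

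z = [0.20 − 1.96·√(2·0.3·0.7/150)] / √(0.24/150 + 0.16/150) = (0.2000 − 0.1037)/0.0516 = 1.86, power 96.9%.

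Variants give 95.9% (continuity corrected), 96.0% (Fisher) and 97.2% (unpooled). The figure is reproduced to within about 2 points. It has no bearing on the imputation, for which the SAP states no number.

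**2. Why correlation matters.** With component success p and independence, P(at least 3 of 4) = 4p³(1−p) + p⁴. With correlation ρ, p is replaced by Φ[(Φ⁻¹(p) + √ρ·z)/√(1−ρ)] and the result averaged over a standard normal z.

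| p | independent | ρ = 0.5 | ρ = 0.7 |
|---|---|---|---|
| 0.3 | 8.4% | 18.7% | 22.2% |
| 0.5 | 31.2% | 40.0% | 42.8% |
| 0.6 | 47.5% | 52.2% | 54.0% |
| 0.7 | 65.2% | 64.9% | 65.6% |
| 0.8 | 81.9% | 77.8% | 77.5% |

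Independence makes the event too rare at low p, is neutral near 0.7 and makes it too common at 0.8. This table is the extreme case; the plan's models keep part of the correlation.

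**3. Simulation closer to the plan.** Four 0–10 components were simulated at Baseline, three further visits and a final visit. Assumed, since the SAP gives none of these: Baseline mean 7, SD 1.5 at Baseline and 2.3 later, between-component correlation 0.5–0.7, visit-to-visit correlation 0.5–0.85, mean improvement 1–5 points. The final visit was imputed either separately, from each component's own history, or jointly, from all histories with correlated residuals. The full ASAS40 rule was then applied. Results at both correlations 0.7:

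| Mean improvement | Component success | True | Separate | Joint | Separate − true |
|---|---|---|---|---|---|
| 1 | 21.0% | 13.8% | 7.1% | 13.4% | −6.7 |
| 2 | 35.7% | 27.5% | 19.0% | 27.2% | −8.5 |
| 3 | 52.9% | 45.6% | 38.6% | 45.3% | −7.0 |
| 4 | 69.7% | 64.8% | 62.1% | 64.8% | −2.7 |
| 5 | 82.9% | 80.7% | 82.2% | 81.8% | +1.5 |

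Over all six pairs of correlations the error of separate imputation is −3.0 to −11.2 points at improvements of 1–3 (component success 18–53%), −0.3 to −4.5 at 4 (69–72%), and +1.1 to +1.9 at 5 (81–86%). At 5 points joint imputation is also 1.0–1.3 too high, so most of that last excess is common to both. The correlation between component changes falls from 0.50 to 0.22–0.31, or from 0.70 to 0.31–0.44.

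**4. Arm level.** Shift = imputed share × shortfall. Shares are assumed, and the same shortfall per imputed subject is applied to both arms. Shortfalls of 5.6, 6.6 and 8.5 points are three of the simulated cases.

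| Imputed, placebo / CZP | Placebo falls | CZP falls | Change in difference |
|---|---|---|---|
| 10% / 10% | 0.6–0.9 | 0.6–0.9 | 0 |
| 30% / 15% | 1.7–2.6 | 0.8–1.3 | 0.15 × 5.6 to 0.15 × 8.5 = 0.8–1.3 |
| 50% / 30% | 2.8–4.3 | 1.7–2.6 | 0.20 × 5.6 to 0.20 × 8.5 = 1.1–1.7 |

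**5. On the odds-ratio scale.** Taking 40% and 20% purely as illustration (they are the ASDAS-MI planning rates), the odds ratio is (0.40/0.60)/(0.20/0.80) = 2.67. With the 30%/15% shifts it becomes (0.392/0.608)/(0.183/0.817) = 2.88 to (0.387/0.613)/(0.174/0.826) = 3.00.

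**6. Size of a joint model.** The components are measured at Baseline and 15 later visits (Section 8.3), so Week 52 has 15 earlier values each. All lags of all components, for the last component imputed, need 4 × 15 + 3 same-visit values + 4 stratum terms = 67 predictors. One component's own history plus the latest previous value of the other three needs 15 + 3 + 3 + 4 = 25, against 15 + 4 = 19 as now listed. In a further simulation, also on assumed SDs and correlations, a joint model with few lags gave 25.4% against a true 26.2%, where separate models gave 17.0%.

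**The case against.** The strongest reply is that separate imputation is inferred. The SAP says the components are imputed before the response is derived; it does not say that the other components are left out, and the reference-based section speaks only of previous measurements. That is correct, and a joint model would not contradict the text. But the predictor lists are explicit and the procedure is written for one variable, so a programmer who follows them runs four separate imputations. The two readings give different rates.

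Three stronger readings are tempting and do not stand.

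- A reader might infer that the imputed components lose their mutual correlation. They do not: each history carries shared signal, and roughly half survives under the assumptions above.
- A reader might infer that derived ASAS40 is always too rare. It is not: the bias fades near component success of 0.7 and reverses above about 0.8.
- A reader might infer that the ASAS40 result itself is overstated. The confirmatory tests, including the Canadian Week 12 primary, use the composite analysis and need no imputation. Two other sensitivity analyses (including observed data, and observed case) use no multiple imputation either.

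It is also fair that unequal discontinuation is assumed. With equal imputed shares and equal shortfalls the shifts cancel in the difference, and no separate size has been shown for Week 12. Finally, a joint model with every lag of every component is not workable on placebo data alone: with 150 placebo subjects and, say, half imputed, about 75 would have to support 67 predictors.

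**Conclusion.** The point holds in a limited form. As written, the SAP gives a stated method that weakens the dependence on which the three-of-four rule rests; this is more than missing detail. Under assumed SDs and correlations, ASAS40 among imputed subjects is about 3–11 points too low at low-to-moderate component success. That is the likely range here, since Section 8.1.3.2 expects treatment to be stopped largely in subjects who are not responding.

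The reach is confined to the MI, reference-based MI and tipping-point analyses of ASAS40, including those supporting the Canadian Week 12 primary. The treatment difference moves by about 1–1.5 points, slightly in favour of CZP, if placebo has about twice the missing data. Nothing in the SAP fixes that ratio. The simulation imputed only the final visit with all earlier visits observed. For subjects missing several visits in a row, each further independent draw would erode the correlation more, so the figures are indicative.

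**What to change.** In Sections 8.1.3.2/8.2.3, 8.2.2.2 and 8.1.3.3, state that the four ASAS components are imputed jointly before ASAS40 is derived. Use sequential regressions in which each component is predicted from its own previous visits, the other components' most recent previous visit, the components already imputed at the same visit, and the terms already listed. Hold the four components together in the MCMC step for intermittent gaps as well. Limit the lags, and say how many, so that the placebo-only model can be fitted.

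The cost is a larger imputation model with fewer lags, and some wording. The SAP notes that double-blind outputs have already been produced, so if separate models were used, these sensitivity tables need a rerun after unblinding, labelled as such and shown beside the existing ones. If joint imputation was used, recording it in the SAP is enough.

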### 8.2.3.1 Multiple imputation of secondary continuous efficacy variables

The continuous BASDAI, BASFI, ASQoL or Nocturnal Spinal Pain scores at each visit will be calculated using the methods described in [Section 8.2.1.2](#), [Section 8.2.1.3](#), [8.2.1.6](#) and [8.2.1.7](#). Missing data (including data excluded due to subjects discontinuing double-blind study treatment) at each visit will be handled via multiple imputation as described below:

1. For subjects with a non-monotone (intermittent) missing pattern, MCMC will be used to impute their missing intermittent scores. This will be done 100 times for each subject including treatment arm, region, MRI/CRP classification and limiting imputation to in range results.

After this step there will be 100 datasets containing all subjects however the only missing data will be a monotone missing data pattern. A variable called “\_imputation\_” will identify each of the 100 imputed datasets.

2. The remaining missing data for all subjects with a monotone missing data pattern will be imputed using regression with treatment arm, region, MRI/CRP classification and measurement from previous visit(s) as explanatory variables. This will be done once for each of the 100 datasets limiting imputation to in range results.
3. The change from Baseline to Week 52 will be calculated using the complete datasets (with no missing data).
4. For each of the 100 imputed datasets (identified by \_imputation\_ variable), an ANCOVA model, where response is the change from Baseline, with Baseline score as a fixed-effect covariate and treatment group, region, and MRI/CRP classification as fixed-effect categorical factors. The estimand of interest here is the difference in BASDAI/BASFI/ASQoL/Nocturnal Spinal Pain, if all subjects tolerate or adhere to double-blind study treatment. In the context of handling missing data in clinical study settings, this has been referred to as “estimand 3” (Mallinckrodt, 2012).
5. The results from these analyses will be combined into a single inference using SAS PROC MIANALYZE.

### 8.3 Analysis of other efficacy variables during the double-blind 52-week treatment period

The efficacy analyses described in this section are not part of the multiplicity-controlled testing procedure described in [Section 8](#). The p-values reported for these analyses will not be adjusted for multiplicity and will be considered nominal. Derivations for these other efficacy variables can be found in [Section 8.3.1](#).

Continuous other efficacy variables will be analyzed using an ANCOVA model including Baseline score as a covariate, and fixed effects for treatment group, region, and MRI/CRP classification. The treatment differences and corresponding 95% CIs will be calculated based upon the adjusted least squares means. Missing values or values observed after discontinuing the double-blind study treatment will be imputed using LOCF. In addition, as described in [Section 4.2.3](#), an observed case analysis will also be performed for subjects still on the original double-blind study treatment. Tables for continuous variables will display descriptive statistics for Baseline, absolute values and change from Baseline at post-Baseline time points.

Categorical other efficacy variables will be analyzed using a logistic regression model with factors of treatment group, region, and MRI/CRP classification (MRI+/CRP+; MRI+/CRP-; MRI-/CRP+). If the logistic regression model is unable to converge, then the MRI/CRP classification variable may be dropped from the model to facilitate convergence. Tables for the binary variables will display the responder rates for the various time points. Analyses will be presented in 2 ways (as described in [Section 4.2.3](#)). First, they will be presented where the denominator is all subjects in the FAS for the given treatment group. This is essentially a NRI approach as subjects who have not achieved the given outcome (whether observed or not) or subjects who discontinue double-blind study treatment are considered as not having responded. Second, the responder rates will be presented for the FAS using Observed Case data. Subjects still on the original double-blind study treatment and with response will be analyzed, with the denominator based on the number of observed values at the given time point.

Continuous other efficacy variables to be analyzed using change from Baseline are:

- BASDAI and BASFI at Weeks 1, 2, 4, 8, 16, 20, 24, 28, 32, 36, 40, 44, 48
- ASDAS at Weeks 2, 4, 8, 12, 16, 20, 24, 28, 32, 36, 40, 44, 48, and 52
- ASQoL at Weeks 1, 2, 4, 12, 24, 36, 48
- Nocturnal spinal pain (NRS) at 1, 2, 4, 8, 16, 20, 24, 28, 32, 36, 40, 44, 48
- Other continuous data from the ASAS components at Weeks 1, 2, 4, 8, 12, 16, 20, 24, 28, 32, 36, 40, 44, 48, and 52:
  - PGADA
  - Total spinal pain (NRS),
  - Morning stiffness as assessed by the average of BASDAI questions 5 and 6
  - BASMI Lateral Spine Flexion
  - CRP

- BASDAI individual questions 1 (Fatigue), 2 (neck, back or hip pain), 3 (pain/swelling in joints other than neck) and 4 (discomfort) at Weeks 1, 2, 4, 8, 12, 16, 20, 24, 28, 32, 36, 40, 44, 48, and 52
- BASMI linear score at Weeks 1, 2, 4, 8, 12, 16, 20, 24, 28, 32, 36, 40, 44, 48, and 52
- Spinal mobility assessments (occiput to wall distance and chest expansion) at Weeks 1, 2, 4, 8, 12, 16, 20, 24, 28, 32, 36, 40, 44, 48, and 52
- Sacroiliitis grading for structural damage at Week 52 (mean of the right and left grade for all readers). Note: LOCF will not be performed as grading is only measured as Baseline and Week 52
- SI joint SPARCC score at Week 52 and ankylosing spine MRI acuity (ASspiMRI-a) in the Berlin modification at Weeks 12 and 52
- ASAS-NSAID use at Weeks 1, 2, 4, 8, 12, 16, 20, 24, 28, 32, 36, 40, 44, 48, and 52  
Thereby, ASAS-NSAID use at a certain week refers to any intake between this week and the previous week.
- Sleep Problems Index II domains of the MOS Sleep scale at Weeks 4, 12, 24, 36 and 48
- Enthesitis (MASES) at Weeks 1, 2, 4, 8, 12, 16, 24, 32, 40, 48, and 52
- Swollen and tender joint counts at Weeks 4, 12, 24, 36 and 52
- PhGADA at Weeks 1, 2, 4, 8, 12, 16, 20, 24, 28, 32, 36, 40, 44, 48, and 52
- SF-36, PCS, MCS and individual domains at Weeks 4, 12, 24, 36, 48, and 52
- EQ-5D VAS at Weeks 4, 12, 24, 36, 48, and 52

Categorical other efficacy variables to be analyzed are:

- ASDAS-MI at Weeks 2, 4, 8, 12, 16, 20, 24, 28, 32, 36, 40, 44, 48,
- ASDAS-CII at Weeks 2, 4, 8, 12, 16, 20, 24, 28, 32, 36, 40, 44, 48, and 52
- [name], HD and vHD at Baseline and Weeks 2, 4, 8, 12, 16, 20, 24, 28, 32, 36, 40, 44, 48, and 52 (Summary statistics provided only)
- BASDAI50 response at Weeks 1, 2, 4, 8, 12, 16, 20, 24, 28, 32, 36, 40, 44, 48, and 52
- ASAS40 at Weeks 1, 2, 4, 8, 16, 20, 24, 28, 32, 36, 40, 44, 48
- ASAS20, ASAS5/6 and ASAS partial remission response at Weeks 1, 2, 4, 8, 12, 16, 20, 24, 28, 32, 36, 40, 44, 48, and 52
- Sacroiliitis grading for structural damage at Week 52 (change from mNY- negative to mNY-positive)
- SI joint SPARCC score <2 at Weeks 12 and 52
- Uveitis flares, IBD exacerbations and Psoriasis exacerbations at Baseline and Weeks 4, 12, 24, 36, 48 and 52 (Summary statistics provided only)
- EQ-5D 5-Item health status at Weeks 4, 12, 24, 36, 48, and 52

For the ‘resource utilization’ variables ‘number of concomitant medical procedures’, ‘number of health care provider consultations not foreseen by the protocol’, ‘number of hospitalizations’, and ‘number of emergency room visits’ descriptive statistics and frequency distributions will be presented for the entire double-blind period.

For the WPS scores, Question 1 responses will be summarized descriptively. Question 2-9 will be summarized by descriptive statistics as well. Treatment comparisons for Question 2 through Question 9 will be performed using a mixed-effect repeated-measures model (MMRM). For each individual question, a separate MMRM will be fitted for the change from baseline, including fixed effects of baseline, treatment, visit, treatment-by-visit interaction and baseline-by-visit interaction, including a random effect of subject and using an unstructured variance-covariance structure. The Kenward-Rogers method will be applied to estimate the denominator degrees of freedom. If convergence problems arise, the covariance structure will be assumed to be autoregressive first order (AR[1]). If that still leads to numerical problems, the more general case, the Toeplitz (TOEP) covariance structure will be used. If all methods above fail to produce a solution, the covariance structure Compound Symmetry (CS) will be used. The least-square means of the treatment difference by visit including 95% confidence intervals and p-values for the test on treatment differences will be summarized.

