#### **4.2.3 Other efficacy variables**

For the analysis of the double-blind 52-week treatment period, other binary efficacy variables will be treated in the same way as the primary analysis of the primary efficacy variable (composite endpoint). That is, a subject will be considered a responder only if the response is achieved and if the subject is still on their randomized double-blind study treatment at the time

when the variable is evaluated. Analyses of other continuous efficacy variables will be based on LOCF. A sensitivity analyses will be performed on all other efficacy variables using observed case analysis as described for the primary endpoint in [Section 4.2.1](#).

For analysis of the Week 156/SFE-WD visit data, binary efficacy variables will be analyzed using the non-responder imputation (NRI) approach; that is, where the denominator is all subjects in the SFE-FAS for the given treatment group. A subject will be considered a responder only if the response criterion of the given variable is achieved. All other subjects will be counted as not responding e.g. subjects who have not achieved the given outcome and all subjects with missing data are set to non-response.

An observed case analysis of binary efficacy variables at Week 156/SFE-WD will be performed. The Observed Case analysis at Week 156, will consider a subject a responder only if the response is achieved. Non-response at Week 156 visit will be counted as non-responders. Early withdrawals or subjects with missing data will be considered missing in this analysis. The sensitivity analysis of the Observed Case analysis at Week 156/SFE-WD will consider a subject as a responder if response is achieved at Week 156/SFE-WD visit such that both subjects with a Week 156 visit (subjects who complete) and subjects with early withdrawal visits and efficacy results meeting the criteria of response, will be counted as a responder. Subjects with missing data will be considered missing in this analysis.

For continuous efficacy variables, the observed data at Week 156/SFE-WD visit will be analyzed. This will summarize efficacy data for completers and subjects with early withdrawal visits during SFE together. In addition, the efficacy data collected at Week 156 for completers only will be summarized.

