### **8.3.1.3 SI joint radiographs**

SI joint radiographs will be read by two reviewers, with adjudication (if applicable), to assess for the presence and severity of sacroiliitis according to mNY criteria for AS in the right and left SI joint separately.

A grading from 0 to 4 will be assigned corresponding to 0 = Normal, 1 = Suspicious but not definite, 2 = Minimal: some sclerosis, minimal erosion, no marked joint space narrowing, 3 = Moderate: definite sclerosis, both sides of the joint with erosions and/or joint space change, and 4 = Ankylosis: complete obliteration of the SI joint with or without sclerosis. Readers will also classify the subjects as mNY-negative or mNY-positive.

A mean grading will be calculated per subject and visit using the four SI grading results (the left and right joint grades read by the 2 readers). If a third adjudication reading is required, then all 6 grades will be used to calculate the mean grade per visit.

If there is disagreement between the 2 readers in the classification of the subject (mNY-negative or mNY-positive), then the 3rd readers adjudication classification will be used for analysis.

Subjects who are positive at baseline (and hence should not have been enrolled) will be excluded from the categorical endpoint analysis of subjects who change from mNY-negative to mNY-positive during the study.

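### In the FAS-denominator (NRI) presentation of Week 52 mNY conversion, baseline mNY-negative subjects who stop double-blind treatment are counted as not having progressed

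*SAP*

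**What the plan says.** Section 8.3 sets one rule for categorical other efficacy variables: logistic regression, with results shown in two ways. On the first: "First, they will be presented where the denominator is all subjects in the FAS for the given treatment group". The SAP calls this essentially NRI. Subjects who have not achieved the outcome, whether observed or not, count as non-responders, and so do those who leave double-blind treatment ("or subjects who discontinue double-blind study treatment are considered as not having responded"). On the second: "Second, the responder rates will be presented for the FAS using Observed Case data". That presentation is limited to subjects still on double-blind treatment.

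Section 4.2.3 carries the same principle: "other binary efficacy variables will be treated in the same way as the primary analysis of the primary efficacy variable".

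The Section 8.3 list of categorical variables includes "Sacroiliitis grading for structural damage at Week 52 (change from mNY- negative to mNY-positive". It is not among the items marked for descriptive summary only.

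Section 8.3.1.3 gives the only special analysis-population rule for this endpoint. Subjects already positive at baseline "will be excluded from the categorical endpoint analysis of subjects who change from mNY-negative to mNY-positive during the study". It says nothing about discontinuation or a missing Week 52 film.

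The continuous version, the mean SI grade, has its own note in Section 8.3: "Note: LOCF will not be performed as grading is only measured as Baseline and Week 52". The categorical version has no matching note.

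**The concern.** NRI is conservative when the outcome is a benefit, such as ASAS40 or BASDAI50, because stopping treatment counts as failure. For mNY conversion the outcome is harm, so the same rule gives the discontinuer the good result. It also overrides evidence. Section 2.3.1 keeps subjects who switch to open-label treatment in the study and invites them to the Week 52 visit. If a film is taken there and shows conversion, the rule still records no conversion.

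Elsewhere the SAP takes account of direction. Section 8.2.1.5 counts subjects without relevant background medication changes, so a discontinuer fails. Section 8.2.2.1 gives uveitis its own event definition. Most other unfavourable items in the Section 8.3 list (high disease activity states, flares, exacerbations) are descriptive only. mNY conversion is unfavourable and goes into the logistic model under the general rule.

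What is at stake is the between-arm comparison in that one presentation. SI joint structural change is a stated objective (Section 2.1.3).

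**Working it through.** The SAP has no figure for this endpoint to reproduce. It gives neither a conversion rate nor a discontinuation rate, so the numbers below illustrate the mechanism under assumed inputs.

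**Inputs**
- Rule: discontinuers count as not having the outcome (Sections 8.3 and 4.2.3).
- Population: FAS, less subjects mNY-positive at baseline (Section 8.3.1.3).
- Group size: 150 per arm (Section 2.4), used only to turn rates into counts.
- Assumed: q, the true conversion rate, and d, the proportion stopping double-blind treatment, with conversion independent of stopping.

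**Formulas**
- Reported rate in an arm = q × (1 − d).
- Odds ratio, CZP versus placebo = [p_C / (1 − p_C)] / [p_P / (1 − p_P)].

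**No true difference, q = 5% in both arms, 40% placebo and 20% CZP stopping**
- Placebo: 0.05 × 0.60 = 0.030.
- CZP: 0.05 × 0.80 = 0.040.
- OR = (0.040/0.960) / (0.030/0.970) = 1.35. The true OR is 1.00.

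**Other assumed inputs**

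| True conversion, placebo / CZP | Stopping, placebo / CZP | Reported, placebo / CZP | True OR | Reported OR |
|---|---|---|---|---|
| 5% / 5% | 20% / 20% | 4.0% / 4.0% | 1.00 | 1.00 |
| 5% / 5% | 60% / 30% | 2.0% / 3.5% | 1.00 | 1.78 |
| 10% / 10% | 40% / 20% | 6.0% / 8.0% | 1.00 | 1.36 |
| 15% / 15% | 40% / 20% | 9.0% / 12.0% | 1.00 | 1.38 |
| 10% / 5% | 20% / 20% | 8.0% / 4.0% | 0.47 | 0.48 |
| 10% / 5% | 40% / 20% | 6.0% / 4.0% | 0.47 | 0.65 |
| 10% / 5% | 60% / 20% | 4.0% / 4.0% | 0.47 | 1.00 |

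Both arms are always understated. The odds ratio moves materially only when discontinuation is unequal.

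**Opposite coding, discontinuer = progressed (q = 5%, 40% / 20%)**
- Placebo: 0.030 + 0.40 = 0.430.
- CZP: 0.040 + 0.20 = 0.240.
- OR = (0.240/0.760) / (0.430/0.570) = 0.42, again with no true difference. The choice of coding direction can therefore decide the result.

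**Precision.** At 150 per arm, 2.0% is 3 subjects and 3.5% is about 5. For 3 versus 5, OR = (5/145) / (3/147) = 1.69. The standard error of its logarithm is √(1/5 + 1/145 + 1/3 + 1/147) = 0.74, giving an approximate 95% CI of 0.4 to 7.2.

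**The case against.** The strongest reply concerns reach, and most of it stands. Section 8.3 already plans an observed-case presentation, and Sections 4.2.3 and 4.2.5 repeat it, so nobody should infer that the miscoded table is the only analysis or that an observed-case analysis is missing. It does leave a gap, because it drops every discontinuer. Neither planned presentation of this endpoint uses a film taken after double-blind treatment stops.

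A reader might also infer that the trial's whole structural-damage comparison is compromised. It is not. The variable named in Section 2.2.1.3 is change in SI grading, which is analysed as a continuous mean grade that NRI does not touch. Nor is any primary or hierarchical secondary conclusion affected, because Section 8.3 labels these p-values nominal.

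A third reply is that the responder wording is generic, written for favourable outcomes, and that a programmer might take remaining mNY-negative as the response. That is possible as intent, but Section 8.3 ties non-response to not achieving the outcome, and the outcome listed is the change to mNY-positive. If the other direction is meant, the SAP must say so, and the 0.42 above shows that this would not be neutral either.

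Finally, the sizes rest on assumptions. It is tempting to say the analysis will show harm from CZP. The documents do not support that. Section 8.1.3.2 lets investigators stop treatment for non-responders and Section 2.4 expects 40% versus 20% response, so more stopping on placebo is plausible, but no rate is given. Even under assumed inputs the counts are small and the interval wide. If placebo stops more, the bias runs against CZP and cannot create a false claim of benefit.

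**Conclusion.** The point holds for the first of the two Section 8.3 presentations of Week 52 mNY conversion. As written, every discontinuer who was mNY-negative at baseline is counted as not having progressed, including one with a film showing conversion. Each arm's rate is understated by the factor (1 − d). The odds ratio is biased when discontinuation differs: 1.35 to 1.38 with no true difference at 40% versus 20% stopping, for q from 5% to 15%, and essentially unbiased when discontinuation is equal. These figures assume both rates and assume that conversion is independent of stopping. The endpoint is nominal and outside the testing hierarchy, and the mean SI grade is unaffected. The rule should be corrected, but it does not threaten the trial's main conclusions.

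**What to change.** In Sections 8.3 and 4.2.3, exempt mNY conversion from the NRI rule and state that conversion is the unfavourable event. As the main analysis, compare conversion by randomized arm among subjects mNY-negative at baseline with a centrally read Week 52 film, regardless of treatment status. Keep the planned observed-case (on-treatment) analysis. Report missing-film-as-converted only as a bounding sensitivity analysis, since it can distort at least as strongly in the other direction when missingness is unequal.

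The cost is a few sentences and one table re-run. There are two downsides to state. The denominator is smaller, and how much smaller depends on whether subjects who switched have a Week 52 radiograph, which the SAP does not say. The all-films analysis also includes placebo subjects who moved to open-label CZP, so it answers a different question from the on-treatment analysis and may dilute a difference.
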